Scheduled Timing	-28 to -1				At time of DC	30 days post last dose	Q12W Year 1 from RAND	Q12W Year 2-3 from RAND	Q24W for Year 4-5 from RAND	Annually for Year 6-7 from RAND	~Q12W	Post-treatment Period: Refer to Sections 8.11.2.1, 8.11.2.2, and 8.11.2.3
Window (days):		+3	±3	±3		+7	±7	±14	±14	±14	±14	
Child-Pugh score	X											Within 7 days prior to C1D1. Thereafter, only if any of the hepatic ECI criteria are met, document the Child-Pugh score with each visit until the hepatic ECIs resolve.

Study Period	Screening Phase	Intervention Phase (Every 3 Weeks and End After 17 Cycles of treatment)			End-of-Treatment	Post-Treatment Visits						Notes
Treatment Cycle		1	2	3 and onwards (up to 17 cycles)	DC	Safety Follow-up ^a	Efficacy Follow-up Visits				Survival Follow-up	Procedures should occur predose on Day 1 of each cycle unless otherwise noted.
Scheduled Timing	-28 to -1				At time of DC	30 days post last dose	Q12W Year 1 from RAND	Q12W Year 2-3 from RAND	Q24W for Year 4-5 from RAND	Annually for Year 6-7 from RAND	~Q12W	Post-treatment Period: Refer to Sections 8.11.2.1, 8.11.2.2, and 8.11.2.3
Window (days):		+3	±3	±3		+7	±7	±14	±14	±14	±14	
AE/SAE Review	X	<----->										AEs: monitored up to 30 days after last dose. SAEs and pregnancy: monitored up to 90 and 120 days after last dose, respectively, or 30 days after last dose if participant starts a new anticancer therapy, whichever occurs first.

Study Period	Screening Phase	Intervention Phase (Every 3 Weeks and End After 17 Cycles of treatment)			End-of-Treatment	Post-Treatment Visits						Notes
Treatment Cycle		1	2	3 and onwards (up to 17 cycles)	DC	Safety Follow-up ^a	Efficacy Follow-up Visits				Survival Follow-up	Procedures should occur predose on Day 1 of each cycle unless otherwise noted.
Scheduled Timing	-28 to -1				At time of DC	30 days post last dose	Q12W Year 1 from RAND	Q12W Year 2-3 from RAND	Q24W for Year 4-5 from RAND	Annually for Year 6-7 from RAND	~Q12W	Post-treatment Period: Refer to Sections 8.11.2.1, 8.11.2.2, and 8.11.2.3
Window (days):		+3	±3	±3		+7	±7	±14	±14	±14	±14	
Laboratory Procedures (LOCAL laboratory)	Clinical laboratory assessments may be conducted anytime within 72 hours prior to the scheduled visit, unless otherwise specified. Procedures/assessments should be performed prior to administration of study intervention.											

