Pregnancy Test – Serum or Urine (WOCBP only)		X	X	X	X	X	X					Refer to Appendix 5 for Contraception Guidance and Appendix 7 for country-specific requirements. Within 72 hours prior to each cycle of treatment and as required by local guidelines up to 120 days after last dose of study intervention or 30 days post dose if new anticancer treatment started, whichever comes first.

Study Period	Screening Phase	Intervention Phase (Every 3 Weeks and End After 17 Cycles of treatment)			End-of-Treatment	Post-Treatment Visits						Notes
Treatment Cycle		1	2	3 and onwards (up to 17 cycles)	DC	Safety Follow-up ^a	Efficacy Follow-up Visits				Survival Follow-up	Procedures should occur predose on Day 1 of each cycle unless otherwise noted.
Scheduled Timing	-28 to -1				At time of DC	30 days post last dose	Q12W Year 1 from RAND	Q12W Year 2-3 from RAND	Q24W for Year 4-5 from RAND	Annually for Year 6-7 from RAND	~Q12W	Post-treatment Period: Refer to Sections 8.11.2.1, 8.11.2.2, and 8.11.2.3
Window (days):		+3	±3	±3		+7	±7	±14	±14	±14	±14	
PT/INR	X		X	X	X	X						Within 7 days prior to C1D1. Then, prior to every cycle starting with Cycle 2. Testing can be performed more frequently if the participant is receiving anti-coagulation medication.

Study Period	Screening Phase	Intervention Phase (Every 3 Weeks and End After 17 Cycles of treatment)			End-of-Treatment	Post-Treatment Visits						Notes
Treatment Cycle		1	2	3 and onwards (up to 17 cycles)	DC	Safety Follow-up ^a	Efficacy Follow-up Visits				Survival Follow-up	Procedures should occur predose on Day 1 of each cycle unless otherwise noted.
Scheduled Timing	-28 to -1				At time of DC	30 days post last dose	Q12W Year 1 from RAND	Q12W Year 2-3 from RAND	Q24W for Year 4-5 from RAND	Annually for Year 6-7 from RAND	~Q12W	Post-treatment Period: Refer to Sections 8.11.2.1, 8.11.2.2, and 8.11.2.3
Window (days):		+3	±3	±3		+7	±7	±14	±14	±14	±14	
T3 (or Free T3), Free T4, and TSH	X		X	X	X							Within 7 days prior to C1D1. Then on Day 1 of every other cycle starting from Cycle 2 (eg, Cycle 2, 4, 6, 8, etc.) and at EOT. Free T3 is acceptable where T3 cannot be determined.

Study Period	Screening Phase	Intervention Phase (Every 3 Weeks and End After 17 Cycles of treatment)			End-of-Treatment	Post-Treatment Visits						Notes
Treatment Cycle		1	2	3 and onwards (up to 17 cycles)	DC	Safety Follow-up ^a	Efficacy Follow-up Visits				Survival Follow-up	Procedures should occur predose on Day 1 of each cycle unless otherwise noted.

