7 DISCONTINUATION OF STUDY INTERVENTION AND PARTICIPANT WITHDRAWAL

7.1 Discontinuation of Study Intervention

Discontinuation of study intervention does not represent withdrawal from the study.

As certain data on clinical events beyond study intervention discontinuation may be important to the study, they must be collected through the participant's last scheduled follow-up, even if the participant has discontinued study intervention. Therefore, all participants who discontinue study intervention prior to completion of the protocol-specified treatment period/vaccination will still continue to be monitored in the study and participate in the study visits and procedures as specified in Section 1.3 (SoA) and Section 8.11.3 (Participants Discontinued from Study Intervention but Continuing to be Monitored in the Study) unless the participant has withdrawn from the study (Section 7.2).

Participants may discontinue study intervention at any time for any reason or be discontinued from the study intervention at the discretion of the investigator should any untoward effect occur. In addition, a participant may be discontinued from study intervention by the investigator or the Sponsor if study intervention is inappropriate, the study plan is violated, or for administrative and/or other safety reasons. Specific details regarding procedures to be performed at study intervention discontinuation are provided in Section 8.1.9.

A participant must be discontinued from study intervention but continue to be monitored in the study for any of the following reasons:

The participant or participant's legally acceptable representative requests to discontinue study intervention

AEs described in the dose modification table that require discontinuation of study intervention (refer to Section 6.6.1).

After prolonged study intervention interruption that prohibits restarting study intervention if agreed upon with the Sponsor.

The participant has a medical condition or personal circumstance which, in the opinion of the investigator and/or Sponsor, placed the participant at unnecessary risk from continued administration of study intervention.

The participant has a confirmed positive serum pregnancy test.

The participant is receiving any prohibited concomitant medication requiring withdrawal (refer to Section 6.5).

Participant has any of the following non-overdose hepatic ECIs:

- ALT $>20 \times \text{ULN}$ (confirmed within 1 week)

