- Drug-related total bilirubin $>10 \times \text{ULN}$
- CP score of >9 points
- Hepatic encephalopathy
- If ascites is not manageable by intervention within 3 days
- Gastrointestinal bleeding suggestive of portal hypertension (eg, esophageal or gastric varices)

Recurrence of either intrahepatic or extrahepatic disease.

Any progression or recurrence of any malignancy, or any occurrence of another malignancy that requires active treatment

Completion of 17 treatments (approximately 1 year) with pembrolizumab versus placebo.

Note: The number of treatments is calculated starting with the first dose.

For participants who are discontinued from study intervention but continue to be monitored in the study, all visits and procedures, as outlined in the SoA, should be completed.

Discontinuation from study intervention is “permanent.” Once a participant is discontinued, he/she shall not be allowed to restart study intervention.

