8.3.1.2 Directed Physical Examination

For clinic visits that do not require a full physical examination as defined in Section 1.3, the investigator or qualified designee will perform a directed physical examination, as clinically indicated, prior to study intervention administration. New clinically significant abnormal findings should be recorded as AEs.

Investigators should pay special attention to clinical signs related to previous serious illnesses, ascites, and encephalopathy.

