8.3.4 Child-Pugh Score

Originally developed in 1973, the Child-Pugh score was used to estimate the risk of operative mortality in participants with bleeding esophageal varices. It has since been modified, refined, and become a widely used tool to assess prognosis in patients with chronic liver disease and cirrhosis. The score considers 5 factors, 3 of which assess the synthetic function of the liver (ie, total bilirubin level, serum albumin, and coagulation parameters [INR or PT]) and 2 of which are based on clinical assessment (ie, degree of ascites and degree of hepatic encephalopathy; see Appendix 14). The investigator or qualified designee will determine the Child-Pugh score during the Screening period within 7 days prior to C1D1 and thereafter as outlined in the SoA.

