8.4.7 Events of Clinical Interest (ECIs)

Selected nonserious and SAEs are also known as ECIs and must be reported to the Sponsor.

Events of clinical interest for this study include:

1. An overdose of Sponsor's product, as defined in Section 8.5, that is not associated with clinical symptoms or abnormal laboratory results.
2. Hepatic ECIs include any of the following events if the events are considered not due to disease progression as judged by the investigator. All of these events (if not associated with disease progression under study) will require holding study treatment, notification of the event(s) to the Sponsor within 24 hours after awareness via electronic media or paper.

For dose interval modification, refer to Section 6.6.1. For guidance related to the diagnosis and management of hepatic ECIs, refer to Section 6.6.2.

- ALT:
 - Among subjects with Baseline ALT $<2 \times \text{ULN}$: ALT $\geq 5 \times \text{ULN}$
 - Among subjects with Baseline ALT $\geq 2 \times \text{ULN}$: ALT $>3 \times$ the Baseline level
 - ALT >500 U/L regardless of baseline level
- Total Bilirubin:
 - Total bilirubin >3.0 mg/dL
- Regardless of laboratory values, hepatic decompensation diagnosed clinically, including:
 - New onset clinically detectable ascites requiring intervention for >3 days

- Hepatic Encephalopathy
- Gastrointestinal bleeding

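### Section 7.1 requires stopping at a Child-Pugh score above 9, but Section 8.4.7 does not list the score as a hepatic ECI and the SoA requires post-baseline scoring only after an ECI

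*Combined protocol and SAP*

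**What the plan says.** **Section 7.1 (Discontinuation of Study Intervention).** The list opens with "A participant must be discontinued from study intervention but continue to be monitored in the study for any of the following reasons". One entry is "Participant has any of the following non-overdose hepatic ECIs", and among its sub-items is "CP score of >9 points". By Appendix 14 that is 10 to 15 points, class C.

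**Section 8.4.7 (Events of Clinical Interest).** Hepatic ECIs are defined by ALT thresholds, by "Total bilirubin >3.0 mg/dL", and by clinically diagnosed decompensation: new ascites needing more than 3 days of intervention, encephalopathy or gastrointestinal bleeding. An event counts only if the investigator judges it not due to progression. The definition mentions no Child-Pugh score, albumin or INR. Section 6.6.2 points to 8.4.7 for the description of these events.

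**Section 1.3 (SoA).** The Child-Pugh row has one scheduled assessment, at Screening. Its note continues: "Thereafter, only if any of the hepatic ECI criteria are met, document the Child-Pugh score with each visit until the hepatic ECIs resolve".

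**Section 8.3.4.** The score is determined "within 7 days prior to C1D1 and thereafter as outlined in the SoA". It adds no assessment of its own.

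**Components.** Chemistry, which includes albumin and total bilirubin (Table 14), is taken on Day 1 of every cycle. For PT/INR the SoA says: "Then, prior to every cycle starting with Cycle 2". Section 8.3.1.2 says of the directed examination: "Investigators should pay special attention to clinical signs related to previous serious illnesses, ascites, and encephalopathy". It also describes that examination as done when clinically indicated.

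**The concern.** A mandatory stopping criterion rests on a score that the schedule does not require until something else has gone wrong. Neither reading of the ECI label closes the gap. If 8.4.7 governs, a score above 9 is not an ECI and prompts no scoring. If 7.1 governs, the score is itself an ECI, and a site must already know it to learn that it should be documented.

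At stake is whether the criterion is applied the same way at every site. All participants enter as Child-Pugh A after resection or ablation, and Section 2.2.1.1 says most HCC arises in cirrhosis, so loss of liver function is a foreseeable safety outcome. A site following the SoA to the letter could keep dosing a participant who meets the 7.1 criterion.

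There is a secondary reporting issue. Post-baseline scores required by the SoA will exist only for participants selected by an event after randomization. One trigger for that selection is ALT, and Sections 2.3 and 6.6.2 describe ALT rises and immune-related hepatitis with this drug class.

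**Working it through.** The plan states no figure to reproduce. The check is whether a score above 9 is possible with no 8.4.7 criterion met.

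**1. Is each laboratory or score limit in 7.1 already inside an 8.4.7 criterion?**
- ALT: 7.1 stops above 20×ULN. In 8.4.7 the trigger is 5×ULN if baseline is below 2×ULN, otherwise more than 3 times baseline. Table 2 caps entry ALT at 5×ULN, so the trigger is at most 3 × 5 = 15×ULN, below 20. Nested.
- Bilirubin: 7.1 stops above 10×ULN if drug-related. This exceeds 3.0 mg/dL whenever ULN is above 3.0 / 10 = 0.3 mg/dL. Nested.
- Encephalopathy, gastrointestinal bleeding and ascites have counterparts in both sections.
- Child-Pugh score: no counterpart in 8.4.7. Not nested.

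**2. Inputs from Appendix 14.** There are five components, each scored 1 to 3. With no 8.4.7 criterion met, bilirubin is at most 3.0 mg/dL (1 or 2 points) and encephalopathy is absent (1 point). Albumin and INR are unrestricted (1 to 3 each). Standard bilirubin bands are assumed, not the altered bands for cholestatic disease.

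**3. Highest score with no ascites.**

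bilirubin 2.0–3.0 (2) + albumin <2.8 (3) + INR >2.3 (3) + ascites none (1) + encephalopathy none (1) = **10**

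This exceeds 9 with no ECI criterion met and no scoring required.

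**4. How close to the edge this is.**
- Same albumin and INR, bilirubin <2.0: 1 + 3 + 3 + 1 + 1 = **9**, which does not exceed 9.
- On anticoagulants (INR fixed at 1 point) with at most mild ascites: 2 + 3 + 1 + 2 + 1 = **9**, also not above 9.
- Entry is at 5 to 6 points, so reaching 10 needs a gain of at least 10 − 6 = 4 points.

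**5. Counts of point combinations with no ECI criterion met.**

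| Ascites allowed (short of the ECI definition) | Combinations | Highest score | Above 9 |
|---|---|---|---|
| None | 2 × 3 × 3 × 1 × 1 = 18 | 10 | 1 |
| Up to mild | 2 × 3 × 3 × 2 × 1 = 36 | 11 | 5 |
| Any grade | 2 × 3 × 3 × 3 × 1 = 54 | 12 | 14 |

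In the order bilirubin, albumin, INR, ascites, encephalopathy, the five in the second row are 1+3+3+2+1, 2+2+3+2+1, 2+3+2+2+1 and 2+3+3+1+1 (each 10), and 2+3+3+2+1 = 11. The third row is an outer limit, because poorly controlled ascites would usually meet the 8.4.7 definition. All are counts of score combinations, not probabilities in patients.

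**6. What is already collected.** From Cycle 2, bilirubin, albumin and PT/INR are available at every cycle. Ascites and encephalopathy are looked for on examination, but no section requires their Child-Pugh category to be recorded each cycle.

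**The case against.** The strongest reply is that the rules are tiered. Section 8.4.7 sets the level at which treatment is held, Section 7.1 sets a higher level at which it stops, and a score above 9 is an escalation limit to be checked once an ECI has started scoring. Section 6.6.2 supports this, since deterioration to Child-Pugh class C is a discontinuation criterion within its management of hepatic events. The reading works for ALT and bilirubin. It fails for Child-Pugh, the item in 7.1 with no counterpart in 8.4.7: step 3 shows that the upper tier can be reached without passing through the lower one.

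The second reply is that safeguards exist apart from the score. Section 8.3.5 has the investigator review every laboratory report. Section 7.1 separately requires stopping when a medical condition places the participant at unnecessary risk. The clinical decompensation item in 8.4.7 applies whatever the laboratory values, and its list is not clearly closed. Nothing forbids calculating the score at any visit. All of this stands. A reader might infer that the criterion can never be reached or cannot act on its own, and the documents do not support that. What is missing is a requirement to score, not the ability to do so.

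The third reply concerns reporting. Child-Pugh shift is not a named safety endpoint in Section 9.4.2, the trial is double-blind, the triggers are the same in both arms, and Table 9 summarizes laboratory shifts by arm. This also stands. The selection problem affects only a comparison of Child-Pugh class, if one is made.

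**Conclusion.** The inconsistency is real and the gap is narrow. Section 7.1 calls a Child-Pugh score above 9 a hepatic ECI and Section 8.4.7 does not. The SoA, to which 8.3.4 defers, requires post-baseline scoring only after an ECI. A participant can therefore meet a mandatory stopping criterion while the plan, followed exactly, asks for no score.

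The size is 1 of 18 combinations with no ascites and 5 of 36 with up to mild ascites short of the ECI definition. How many participants this would be cannot be derived from the documents. It rests on the Appendix 14 bands and on 8.4.7 as printed.

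Two stronger inferences should be resisted. One is that falling albumin and rising INR alone carry participants past the limit unseen: without at least 2 bilirubin points or some ascites the total stops at 9. The other is to count unscored class B states, which are 13 of the 18 combinations, as missed stops. Class B is not a stopping criterion in 7.1.

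There is no effect on sample size, power or type I error.

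**What to change.** Reconcile Sections 1.3, 7.1, 8.3.4 and 8.4.7 on two points:

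1. State consistently whether a Child-Pugh score above 9 is a hepatic ECI.
2. Make the assessments required by the SoA sufficient to apply the stopping criterion that 7.1 already states.

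The clinical rule and the timing of scoring are for the sponsor to decide.

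If Child-Pugh class is reported by arm, add a note that post-baseline scores documented under the current SoA exist only for participants who already had a hepatic ECI.

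The cost is a few lines of text. No new blood sample is needed, because bilirubin, albumin and PT/INR are already taken at each cycle from Cycle 2. The small added burden is recording ascites and encephalopathy category wherever a score is required.

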6.6.2 Guidance for Management of Hepatic Events of Clinical Interest

Hepatic ECIs (HECIs) have been described in Section 8.4.7. All of these HECIs will require holding study intervention and notification of the Sponsor within 24 hours. All cases of retreatment after interruption of study intervention for HECI must be reported to the Sponsor and recorded in the database.

Immediate assessment if HECI:

All Participants

- All participants should be considered for evaluation according to the directions below within 72 hours of the alert for a non-overdose ECI. For laboratory assessments of HECIs, central laboratory is preferred; local laboratory is acceptable if central laboratory is not available.
- Procedures:
 - Consider obtaining a consultation with a hepatologist
 - Obtain a workup for hepatitis if there is no underlying hepatitis, including hepatitis A, B, C, D, E, Epstein-Barr virus, and cytomegalovirus
 - Assess for ingestion of drugs/supplements with hepatotoxic potential
 - Assess for alcohol ingestion
 - Assess for potential bacterial infection, biliary obstruction, or occult gastrointestinal bleeding
 - Repeat ALT, AST, total bilirubin, direct bilirubin, alkaline phosphatase, glutamyl transpeptidase, international normalized ratio (INR), and complete blood count with differential
 - Measure HCV RNA viral load
 - HBV DNA, HbsAg, HbeAg, anti-HBc (total and IgM), anti-Hbe, and anti-HBs regardless of prior HBV status (Note: participants should be questioned about compliance with the use of antiviral agents)
 - Other laboratories or imaging studies as clinically indicated
 - Consider liver biopsy if indicated

HCC patients are at risk for a range of complications that can cause hepatic laboratory abnormalities with or without clinical decompensation. Those with a history of chronic HCV or HBV infection also have the potential to experience virologic flares. Immune-related hepatitis has been observed in approximately 1% of participants who received pembrolizumab. The following section provides further guidance on the diagnosis and management of potential hepatic complications among HCC participants in this study.

Management of HECI for Pembrolizumab/Placebo

	Diagnosis	Management

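### Child-Pugh above 9 is a mandatory permanent stop in Section 7.1, but after screening no score is required until another hepatic ECI has already held dosing

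*Combined protocol and SAP*

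**What the plan says.** Section 7.1 lists the reasons for which study intervention must be stopped. One group opens with "Participant has any of the following non-overdose hepatic ECIs" and includes "CP score of >9 points". The stop is final: "Once a participant is discontinued, he/she shall not be allowed to restart study intervention".

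The Child-Pugh row of the Schedule of Activities (SoA, Section 1.3, Table 1) carries a single mark, at Screening. Its note then says: "Thereafter, only if any of the hepatic ECI criteria are met, document the Child-Pugh score with each visit until the hepatic ECIs resolve". Section 8.3.4 adds no time points; the score is due "within 7 days prior to C1D1 and thereafter as outlined in the SoA".

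Section 8.4.7 defines the hepatic ECIs. It gives three ALT criteria, "Total bilirubin >3.0 mg/dL", and a clinical group that opens with "Regardless of laboratory values, hepatic decompensation diagnosed clinically, including" and names ascites needing more than 3 days of intervention, encephalopathy and gastrointestinal bleeding. It has no criterion for Child-Pugh, albumin or INR. On consequences, Section 6.6.2 says: "All of these HECIs will require holding study intervention and notification of the Sponsor within 24 hours".

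**The concern.** A mandatory stop needs its input to be available when the dosing decision is made. Here the SoA requires the score only after a hepatic ECI, and by then dosing is on hold. If a score above 9 is itself taken as an ECI criterion, following the label in 7.1, the instruction becomes circular: the site needs the score to know whether to score.

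This matters because, of the six hepatic stops in 7.1, only the Child-Pugh one responds to albumin and INR. The other five concern ALT, bilirubin, encephalopathy, ascites and portal-hypertensive bleeding. A participant who lost synthetic function without any of those events could meet a mandatory permanent stop while a site following the SoA had no score due before the next dose. Because 7.1 and 8.4.7 disagree on whether the finding is a hepatic ECI, sites could also differ on whether it calls for a hold and 24-hour notification.

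**Working it through.** The plan states no figure to reproduce. The check asks which scores above 9 can occur without a listed 8.4.7 criterion.

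**Inputs.** Appendix 14 scores five components from 1 to 3 points:
- Bilirubin (mg/dL): <2.0, 2.0–3.0, >3.0.
- Albumin (g/dL): >3.5, 2.8–3.5, <2.8.
- INR: <1.7, 1.7–2.3, >2.3. It scores 1 point for anyone on anticoagulants.
- Ascites: none, mild, moderate to severe.
- Encephalopathy: none, grade I–II, grade III–IV.

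The stop is a total above 9, that is, 10 or more (class C).

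**Step 1: all patterns above the threshold.** There are 3^5 = 243 patterns, with totals from 5 to 15, symmetric about 10. Exactly 51 total 10, so (243 − 51)/2 + 51 = 96 + 51 = 147 exceed 9.

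**Step 2: remove those that a listed criterion catches.** Three-point bilirubin is the 8.4.7 bilirubin criterion, and encephalopathy is listed directly. An ECI-free pattern therefore has bilirubin at 1 or 2 points and encephalopathy at 1. Albumin and INR are unrestricted. ALT is assumed to be below its criteria, with no gastrointestinal bleeding.

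| Handling of ascites | Patterns above 9 with no listed ECI (bilirubin/albumin/INR/ascites/encephalopathy points) | Count |
|---|---|---|
| Any ascites counts as an ECI | 2/3/3/1/1 = 10 | 1 of 147 |
| Mild ascites needing ≤3 days of intervention is not an ECI (assumption) | the above, plus 1/3/3/2/1 = 10, 2/2/3/2/1 = 10, 2/3/2/2/1 = 10, 2/3/3/2/1 = 11 | 5 of 147 |

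So 147 − 5 = 142 to 147 − 1 = 146 of the 147 patterns meet a listed ECI, which holds dosing and triggers scoring.

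**Step 3: a concrete case.** Bilirubin 2.5 mg/dL (2), albumin 2.6 g/dL (3), INR 2.4 without anticoagulants (3), no ascites (1), no encephalopathy (1): 2 + 3 + 3 + 1 + 1 = 10. Section 7.1 requires a permanent stop, no listed 8.4.7 criterion is met, and the SoA requires no score.

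**Step 4: anticoagulated participants.** With INR fixed at 1 point, the ECI-free maximum is 2 + 3 + 1 + 1 + 1 = 8 without ascites and 2 + 3 + 1 + 2 + 1 = 9 with mild ascites. Neither exceeds 9, so the gap does not arise.

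**Step 5: visits affected.** A participant with no hepatic ECI has no required score at Cycles 2 to 17, which is 17 − 2 + 1 = 16 dosing visits.

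**The case against.** The strongest reply is that hold-then-stop is the intended structure. Entry ALT is at most 5×ULN (Table 2), so the 8.4.7 criterion of more than 3 times baseline is passed by 15×ULN at the latest, before the 7.1 stop at 20×ULN. Bilirubin above 10×ULN likewise exceeds 3.0 mg/dL for any ULN above 0.3 mg/dL. The management table in 6.6.2 uses class C in the same way, as a reason to discontinue during a hold for immune-related hepatitis. This stands: turning a hold into a stop is a real function, and event-triggered scoring is not wrong in itself. The difference is that for ALT and bilirubin the same quantity triggers the earlier hold. Albumin and INR trigger none, so the Child-Pugh stop can be reached without one.

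The second reply is that the case in the working would hardly go unnoticed. Chemistry, which includes albumin and bilirubin, and PT/INR are done every cycle from Cycle 2. The directed examination looks for ascites and encephalopathy. Section 8.3.5 obliges the investigator to review each laboratory report and document the review. The decompensation list in 8.4.7 is open-ended, so a clinical diagnosis would itself be an ECI. Section 7.1 also requires, and does not merely permit, a stop when the investigator and/or Sponsor judges the participant to be at unnecessary risk. Nothing forbids calculating a score earlier. All of this stands. A reader might infer that liver function goes unmonitored during dosing; the documents do not support that. What is missing is a requirement to calculate the score on which one mandatory rule depends.

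The mild-ascites assumption is also open to challenge. Appendix 14 describes mild ascites as controlled by medication, and treatment of new ascites beyond 3 days is already an ECI. Without that assumption the count is 1, not 5.

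**Conclusion.** The point holds in a limited form, at low severity. Sections 7.1 and 8.4.7 disagree on whether Child-Pugh above 9 is a hepatic ECI. As scheduled, the score is not required before any dose unless another hepatic ECI has already held treatment. The listed criteria miss 1 of 147 patterns above 9, or 5 of 147 under the mild-ascites assumption.

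These counts are not probabilities. The documents give no event rate, and the missed states are probably rare among participants who enter in class A (5 to 6 points).

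Two stronger readings should be resisted. The stop is not without effect, because it still converts holds into permanent stops. Nor does the one-year survival in Appendix 14 (45% for class C against 100% for class A) show harm from a dose given in the unscored state: it is general prognosis in chronic liver disease.

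**What to change.** Make two edits together:
- **SoA, Child-Pugh row:** replace the ECI-only condition with a score calculated before dosing at each cycle from Cycle 2, using the bilirubin, albumin, PT/INR and directed examination already scheduled.
- **Section 8.4.7:** add a Child-Pugh score above 9 to the hepatic ECI list, to match 7.1. On its own this edit would leave the circularity in place.

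If dosing is complete, derive the score from recorded laboratory and examination data and list any dose given at a score of 10 or more.

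The cost is up to 16 calculations per participant and one eCRF field, with no new tests or visits. The few additional hepatic ECIs would carry 24-hour Sponsor notification and, under Table 6, fall in the category that requires regulatory reporting.
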